Data will be collected and entered directly into the eCRF system. Each participating site will have access to the data of its own enrolled patients. All sites will be fully trained on using the on line system, including eCRF completion guidelines and other help files. Sites will be responsible for entering patient data into the secure internet-based eCRF. Investigators and other site personnel will access their account with a unique username and password. All eCRFs should be completed by designated and trained personnel, as appropriate. Each eCRF has to be reviewed and electronically signed and dated by the investigator.

File Retention and Archiving

To enable evaluations and/or audits from regulatory authorities, the investigator agrees to keep records, including the identity of all participating patients, all original signed informed consent forms, and source documents. The records should be retained by the investigator according to local regulations, or as specified in the study contract, whichever is longer.

Each site will receive a study site file at study initiation which contains all documents necessary for the conduct of the study that is updated throughout the study. This file must be available for review in the event the site is selected for monitoring, audits, or inspections and must be safely archived for at least 10 years or according to local legislation respectively after completing the participation in the study.

Documents to be archived include the patient identification list, screening log and the signed informed consent form (ICF).

STATISTICAL CONSIDERATIONS

Sample Size

In order to

- achieve information on the clinical course of high, intermediate and low-risk patients with acute pulmonary embolism,
- observe a number of cases with intermediate / low-risk PE died at 30 days from diagnosis and adequate to evaluate around 10 variables able to possibly predict poor patients' outcome by means of logistic regression analysis

expecting an incidence of death of 3% and 0.5% for patients with intermediate or low-risk, respectively, it is estimated that 2100 patients with intermediate pulmonary embolism and 2500 with low-risk pulmonary embolism should be included in the study. In the same time frame, it is estimated that around 400 patients with high-risk pulmonary embolism will be observed. The expected mortality in these patients is 10-15%. According to these estimates, we would be able to have about 100 deaths in study patients and this will empower assessment of independent predictors of death. Besides already known predictors (hypotension, right ventricle dysfunction – imaging and BNP – and increased troponin), the role of comorbidities and clinical features as well as adherence to current guidelines on pulmonary embolism (risk stratification adequate, appropriateness of acute treatment) as determinants of prognosis will be assessed. The same features will be tested as predictors of death or clinical deterioration.

The inclusion of patients in each risk category (low, intermediate and high risk for death) will be stopped when the predicted number of patients is complete. An alert signal will appear in the e-CRF once the estimated sample is completed.

Planned analyses

The following analyses are planned:

1. Final analysis on the data
2. Three data snapshots of the study data are planned and will be analysed before the final analysis will take place after data base lock:
 1. Snapshot: Q4 2018
 2. Snapshot: Q3 2019
 3. Snapshot: Q1 2020

All analyses will contain a summary of all data plus a summary of data per patient groups.

The writing of the SAP for the study will start immediately after the finalisation of the observational plan and a version 1.0 of the SAP will be available before the start of the study. If the SAP needs to be revised for a snapshot or the final analysis, the adaptation will always be finalised and signed before the extraction of data for the respective snapshot or the final data base lock, respectively.

Statistical methodology

All variables collected in the CRFs as well as all derived parameters will be used in the statistical analysis. Categorical variables will be summarized by the number and percentage (%) of patients in each category. Continuous variables will be summarized using number of non-missing observations, mean, SD, median, first quartile and third quartile, minimum and maximum values. The 95% CIs will also be provided for selected variables.

The association of clinical characteristics with death and death or clinical deterioration will be evaluated by means of univariate and multivariable logistic and multinomial logistic regression models, respectively. Variables with a p-value < 0.10 at the univariate analysis will be considered for the multivariable model and covariates will be selected for the final model by means of a step-wise selection procedure.

A time-to-event analysis will be also performed. Kaplan-Meier plots will be generated where applicable to characterize the risk over time for each outcome.

Time-to-event variables will be analysed via a Cox proportional hazard regression model presenting hazard ratios and corresponding 95% confidence intervals and p-values for comparisons of the pre-defined subgroups.

Analysis of primary endpoint

For the primary endpoint, the overall rate of in-hospital deaths and deaths at 30 days from diagnosis of pulmonary embolism (including the 95% confidence interval) will be presented.

Furthermore, the following subgroups will be descriptively compared:

- patients admitted in Cardiology, Emergency or Internal Medicine Departments
- patients at low, intermediate or high risk for death according to ESC guidelines definition.

Further comparisons of the above subgroups will be done via Cox proportional hazard regression models presenting hazard ratios and corresponding 95% confidence intervals. If relevant differences in Baseline characteristics are detected, these variables will be added to the model as additional covariates.

Analysis of secondary endpoints

The analyses will follow the above outlined analysis of the primary endpoint. Absolute and relative frequencies of death or clinical deterioration at 30 days from diagnosis of pulmonary embolism and of pulmonary embolism-related death or clinical deterioration at 30 days from diagnosis of pulmonary embolism (including the 95% confidence interval).

For all secondary endpoints, summary statistics, frequencies and rates (including the 95% confidence interval) will be presented overall and within the different patients' groups (see 9.3.1 for details). Kaplan-Meier estimates will be calculated for the occurrence of death or clinical deterioration at 30 days from diagnosis of pulmonary embolism and of pulmonary embolism-related death or clinical deterioration at 30 days from diagnosis of pulmonary embolism.

In analogy to the primary endpoint, comparisons of patients will be performed for the following subgroups

- patients admitted in every-day clinical practice in Cardiology, Emergency or Internal Medicine Departments
- patients at low, intermediate or high risk for death according to ESC guidelines definition.

For all secondary endpoints results of the Cox proportional hazard regression models will be evaluated as well (hazard ratios and corresponding 95% confidence intervals). If relevant differences in baseline characteristics are detected, these variables will be added to the model as additional covariates. Further data like patient characteristics or laboratory data will be summarized as appropriate, i.e. by means of absolute numbers and percentages or by means of standard statistics.

Furthermore, it will be looked at safety endpoints

- major bleedings
- clinically relevant non-major bleedings .

Definition of adherence

Firstly, the number of indicators that each patient will have met will be counted and divided by the total number for which the patient was eligible, obtaining the proportion of adherence.

The adherence score is defined as the ratio of the diagnostic tests/prognostic evaluations/treatment actually prescribed to those that should theoretically have been prescribed. Adherence will be calculated separately for each step (diagnosis/prognostic stratification/treatment) and globally for the overall patient's management. The theoretical diagnostic/prognostic/treatment/global scores will be calculated for every patient, taking into account diagnostic/prognostic/treatment eligibility criteria, guideline-based contraindications to tests/drugs or treatments.

We define as adherent to the care pathway a patient with a proportion of met indicators equal or greater than 80%. Sensitivity analyses will be performed at different cut-offs, and considering adherence

as an ordinal and a continuous variable. A directed acyclic graph will be constructed (DAG) (26) to represent assumptions regarding the underlying causal relationships between guideline adherence, survival and a set of clinical and socioeconomic variables. The DAG utilizes these assumptions to select the potential confounders, rather than relying on the statistical associations observed in the data. The selected confounders are then used in the statistical analysis aiming at evaluating the 'causal' impact of receiving a care adherent to guidelines on survival.

The adherence score will be corrected:

- for diagnosis by the sequence of tests over time.
- for treatment by sequence of different anticoagulant agents according to validated regimens and use of recommended dosages.

Diagnosis

The score will be calculated for each patient by summing the points attributed as follows: 0.5 points for use of non validated sequence or 1 point for use of recommended sequence of diagnostic tests. Non-administration of recommended tests due to specific contraindications or intolerance (i.e. allergy to contrast media) will be scored as adherence to guidelines.

The score ranges from 0 (very poor) to 1 (excellent) and we define three levels of adherence: good adherence (score =1); moderate adherence (score >0.5 to <1) and poor adherence (score ≤0.5).

In this study, the term 'adherence' relates solely to physicians following guidelines, not to patient compliance.

Risk stratification

The score will be calculated for each patient by summing the points attributed as follows: 0.5 points for use of not recommended tests or 1 point for use of recommended tests.

The score ranges from 0 (very poor) to 1 (excellent) and we define three levels of adherence: good adherence (score =1); moderate adherence (score >0.5 to <1) and poor adherence (score ≤0.5).

In this study, the term 'adherence' relates solely to physicians following guidelines, not to patient compliance.

Treatment

The score will be calculated for each patient by summing the points attributed as follows: 0 points for non-prescription of a given treatment (i.e. thrombolysis) in the absence of contraindications, 0.5 points for use of non validated regimen or 1 point for use of validated regimen. Non-administration of recommended drugs due to specific contraindications or intolerance will be scored as adherence to

guidelines. The score ranges from 0 (very poor) to 1 (excellent) and we define three levels of adherence: good adherence (score =1); moderate adherence (score >0.5 to <1) and poor adherence (score ≤0.5). In this study, the term 'adherence' relates solely to physicians following guidelines, not to patient compliance or persistence.

QUALITY CONTROL

This study will be conducted according to the rules of 'Good Clinical Practice' (GCP).

The physician will comply with the confidentiality policy and with the observational plan described in the protocol. The physician is ultimately responsible for the local conduct of all aspects of the study and verifies by signature the integrity of all data.

All monitoring details will be described in a separate Clinical Operations Plan (COP).

On-site monitoring will be performed according to a risk-based approach. During on-site monitoring the monitor will verify 100% of informed consent documentation and a selected, limited set of very relevant variables will be checked on the patient's medical records.

Data quality checks will be performed on an ongoing regular basis. Queries will be raised by the responsible CRO and shall be answered by the site in due course. The purpose is to ensure that the rights of the patients are protected and that the reported data is accurate and complete.

An independent adjudication committee will centrally review documentation on study outcome events in order to allow to definitely adjudicate the cause of in-hospital and 30 day deaths.

Limitations of the Research Methods

As this study aims at collecting real-world evidence, some limitations common to non-interventional studies apply. In addition, the following aspects need to be considered:

- Although sites will be selected to guarantee representativeness for their medical activities as much as possible, sites also need to have sufficient capabilities, interest and capacities to participate in the study and they need to be able to comply with the study protocol at the site. This may influence the sites' representativeness in some regions.
- Eligible patients not giving their informed consent to participate in the study cannot be enrolled. Therefore this may impact the consecutive enrolment at a site.
- For rating adherence to ESC guidelines, there might be differences due to different type of sites, namely hospital and departments. The respective tables will be stratified by type of site to detect these discrepancies (if any) and to allow for a careful and appropriate interpretation of the results.
- Also differences between the regions might occur, especially when rating adherence. Therefore, especially for adherence the analysis by region will be carefully looked at. In case that there will be mentionable differences the interpretation has to be very careful.

- As the study is non-interventional, only data from the clinical routine treatment can be obtained. Therefore, some information may be missing or unavailable and comparisons between treatments concerning efficacy and/or safety un-appropriate. This needs to be taken into account when data are analysed and reported.

No explicit non-eligibility criteria are defined to avoid selection of patients and thus violation of the 'real-life' principle.

PROTECTION OF HUMAN SUBJECTS

Review by Ethics Committees/Competent Authorities

Notification to or approval by institutional ethics committees (IECs) and competent authorities (CAs) or other organizations will be performed as required by national and local regulations in the participating countries before commencement of enrolment at a study centre.

All treatments of patients included in this study are local standard of care and occur as part of the routine clinical practice. The study is non-interventional and does not foresee any change of treatment nor additional examinations apart from the standard of care.

Patient Information, Informed Consent

Written Informed Consent (ICF) will be obtained from all patients before or on baseline data collection point and not thereafter.

The ICF should be approved by the Independent Ethics Committee (IEC) prior to being provided to potential patients.

The patient's written informed consent will be documented in the patient's medical records of the investigator. Two ICF forms should be signed and personally dated both by the patient and by the investigator who conducted the informed consent discussion. One original signed ICF should be retained at the study centre (preferably in the patient's medical records). The second original of the signed consent form should be provided to the patient. The date informed consent was given will also be recorded in the Case Report Forms (eCRF).

In addition, the patient has to agree with his/her signature to provide his/her contact details (address, phone number, email) to the investigator to allow his/her for future study contacts for follow up. The patients must declare with a signature to agree to the follow-up by calls or email.

Data Protection

The patients' privacy will be kept according to the requirements of Directive 95/46 EC and national legislation for data protection. Data will be collected in a pseudonymous way. An identification

number assigned to each patient will be used in lieu of the patient's name to protect the patient's identity.

All patient contact information required for follow-up calls will be kept strictly confidential and will only be accessible by the site personnel. This personalized data will be stored separately from the project specific database and the data will be destroyed after the completion of the study.

Only authorised personnel at the site has access to the identification list or original source documents (medical records). Representatives of the sponsor, the contract research organisation (CRO), and authorities are allowed access in case of audit or inspection or for monitoring purposes. The patient will agree to this by signing a respective statement on the ICF.

Numbering and Identification of Patients

A unique identification number (patient ID) will be assigned to each patient when reporting data in the eCRF or on the paper patient questionnaires.

At each study centre a patient identification list will be kept linking the identification number to the patient's identity.

Assessments

The investigators will be instructed about the correct documentation of the required variables for each patient in the eCRF. These data are available as part of the routine treatment. All examinations performed depend on the discretion and clinical routine of the physician. No diagnostic or monitoring procedures are applied to the patients in the study others than those performed as standard of care.

STUDY ORGANIZATION

The study will be coordinated by the University of Perugia (Sponsor) and the Steering Committee.

The Steering Committee will be composed by three members from the Sponsor, 4 members from Associazione Nazionale Medici Cardiologi Ospedalieri (ANMCO), 2 members from Società Italiana Medicina Emergenza Urgenza (SIMEU) and 2 members from Federazione Assistenti Dirigenti Ospedalieri medicina Interna (FADOI).

An independent adjudication committee will be designated to definitely adjudicate the cause of death.

FEASIBILITY

The study is promoted by the University of Perugia (Sponsor) and ANMCO, with the collaboration of SIMEU and FADOI.

About 200 hospital- in Italy are planned to participate in the study. For comparisons, the following specialties are pre-specified:

Cardiology (around 80 sites)

Emergency (around 40 sites)

Internal Medicine (around 80 sites).

Sites who have not recruited any patient in the first 6 months after site initiation can be excluded from further participation.

The total study period from first patient in to last patient out is 25 months. The individual start per center depends on Ethical Committee and Institutional review Board approvals and will range approximately from Q1 2018 to Q2 2018.

The patient recruitment period consists of 24 months, followed by a 1 month follow up period per patient, summing up to 25 months.

PLANS FOR DISSEMINATING AND COMMUNICATING STUDY RESULTS

For publishing the study results a separate publication plan will be set up by the scientific Steering Committee. The final study report will be made publicly available within 6 months after LPO. Full manuscripts are planned to be submitted for the baseline data and for final data.

Publication of sub-studies and secondary analyses should have the approval of the Steering Committee. Aside from the main publication, participating investigators in the study can propose ancillary analyses and related second level publications. Such publications may be produced by a dedicated team of authors in common agreement with and governed jointly by the SC of the study.

DOCUMENTATION AND ARCHIVING

The sponsor is responsible for archiving study specific documentation (Observational Plan, amendments, copy of eCRF burned on CD, Final Report and Database) for at least ten years. Archived data may be held on electronic record, provided that a back-up exists and that hard copies can be obtained, if required.

The investigator is responsible for archiving the patient identification list, all signed ICFs, copy of his eCRF burned on a CD for at least ten years and in accordance with local legislation.

Physicians are obliged to keep patient files according to national requirements.

Registration

This study will be listed in in public study database which meets International Committee of Medical Journal Editors requirements.

PREMATURE TERMINATION OF THE STUDY

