- Adherence to current guidelines on the management of acute pulmonary embolism released by the European Society of Cardiology concerning diagnosis, risk stratification, hospitalization and treatment. These items will be evaluated in the overall study population and compared between patients admitted in every-day clinical practice in Cardiology, Emergency or Internal Medicine Departments.

Primary study outcome

The co-primary study outcomes are

- in-hospital death and
- death at 30 days from the diagnosis of pulmonary embolism.

Secondary study outcomes

The secondary study outcome are:

- death or clinical deterioration at 30 days from the diagnosis of pulmonary embolism.
- pulmonary embolism-related death or clinical deterioration at 30 days from the diagnosis of pulmonary embolism
- Adherence to current guidelines on the management of acute pulmonary embolism released by the European Society of Cardiology regarding diagnosis, risk stratification and treatment.

For all patients, the cause of death will be reported as assessed by the attending physician and classified as:

- Unexpected
- Pulmonary-embolism related
- Due to bleeding
- Due to cardiovascular events other than pulmonary embolism
- Due to cancer
- Other non-cardiovascular causes

Pulmonary embolism-related death is defined as i) death where pulmonary embolism is the most probable cause or ii) based on objective diagnostic testing performed before death or iii) as assessed at autopsy (autopsy is not mandatory).

Documentation on study outcome events (in-hospital and 30 day deaths) will be centrally collected in order to allow an independent adjudication committee to definitely adjudicate the cause of death.

Clinical deterioration is defined as the occurrence of at least 1 of the following (25):

- (iv) the need for cardiopulmonary resuscitation;
- (v) systolic blood pressure <90 mm Hg for at least 15 minutes, or drop of systolic blood pressure by at least 40 mm Hg for at least 15 minutes, with signs of end-organ hypoperfusion (cold extremities, or urinary output <30 mL/h, or mental confusion);
- (vi) the need for catecholamine infusion (except for dopamine at a rate of <math><5 \mu\text{g kg}^{-1} \text{min}^{-1}</math>) to maintain adequate organ perfusion and a systolic blood pressure of >90 mm Hg.

Adherence to ESC guidelines 2014 will be assessed concerning:

- diagnosis
- risk stratification
- treatment

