- global management (the composite of diagnosis, risk stratification and treatment)

Six process indicators were selected, based on recommendations from ESC guidelines (6). The indicators are:

- (1) Time from diagnosis to initiation of anticoagulant treatment. The time of CT angiography or of lower limbs ultrasonography will be considered as time of diagnosis.
- (2) Number of diagnostic tests applied and their order within the diagnostic work-up based on estimated pre-test probability of pulmonary embolism.
- (3) Type, number and timing (within 24 hours) of tests performed for prognostic assessment.
- (4) Use of systemic thrombolysis or percutaneous manoeuvre associated with intravenous heparin for at least 48 hours in hemodynamically unstable patients.
- (5) home treatment or short hospital stay (<48 hours) in patients with low-risk pulmonary embolism
- (6) The number, dose and sequence of antithrombotic agents according to currently validated regimens.

Safety Objective

The safety objective of this study is to collect and evaluate real-world safety data on bleeding events in patients with acute pulmonary embolism.

Safety Outcomes

The primary safety outcome is:

- Major bleeding according to ISTH definition, occurring up to 30 days from the diagnosis of index pulmonary embolism.

Major bleeding, defined (as per ISTH guidelines), as acute clinically overt bleeding (i.e. bleeding that is visualized by examination or radiologic imaging) associated with one or more of the following:

- decrease in hemoglobin of 2 g/dl (1.2 mmol/L) or more;
- transfusion of 2 or more units of packed red blood cells;
- bleeding that occurs in at least one critical site [intracranial, intra-spinal, intraocular (within the corpus of the eye; thus, a conjunctival bleed is not an intraocular bleed), pericardial, intra-articular, intramuscular with compartment syndrome, or retroperitoneal];
- bleeding that is fatal;
- bleeding that necessitates acute surgical intervention

Major bleeding events will also be further sub-classified as life-threatening or non-life threatening. A life-threatening major bleed is defined as a bleeding event that is either intracranial or is associated with haemodynamic compromise requiring intervention.

The secondary safety outcome is:

- Clinically relevant non-major bleeding.

Clinically relevant non-major bleeding event defined as acute clinically overt bleeding that does not meet the criteria for major and consists of:

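### The definition of a life-threatening major bleed leaves out fatal bleeding, so a fatal extracranial bleed without haemodynamic compromise requiring intervention is labelled non-life threatening

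*Protocol*

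**What the plan says.** The Safety Outcomes section of the Protocol makes three statements that have to be read together.

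- Major bleeding requires acute, clinically overt bleeding plus at least one of five features: a haemoglobin fall, transfusion, a critical site, a fatal outcome, or the need for acute surgery. The fatal criterion, "bleeding that is fatal", stands alone. The critical sites include several outside the skull, among them "pericardial, intra-articular, intramuscular with compartment syndrome, or retroperitoneal".
- All major bleeds are then divided: "Major bleeding events will also be further sub-classified as life-threatening or non-life threatening". There are two classes and no third.
- The upper class is defined by two alternatives: "A life-threatening major bleed is defined as a bleeding event that is either intracranial or is associated with haemodynamic compromise requiring intervention".

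The Synopsis repeats the two-way split without defining life-threatening. Separately, under Secondary study outcomes, cause of death has a category "Due to bleeding", and an independent committee adjudicates the cause of in-hospital and 30-day deaths.

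**The concern.** The definition has an either/or form, so its list is closed, and fatality is not on it. A bleed can qualify as major because it killed the patient and still fail both conditions for life-threatening. Since the split has only two classes, it must then be called non-life threatening. The label contradicts the fact that made the event major.

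What is at stake is how the severity split reads. The Protocol states its aim here as follows: "The safety objective of this study is to collect and evaluate real-world safety data on bleeding events in patients with acute pulmonary embolism". A severity table built faithfully on the stated rule could list a death among the non-life threatening events, and a reader would reasonably take that row to contain no deaths.

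**Working it through.** The plan gives no figure to reproduce and no arithmetic applies. The check is a logical one on the definitions in Safety Outcomes.

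**Definitions, for acute overt bleeds**

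- Major = haemoglobin fall OR transfusion OR critical site OR fatal OR acute surgery.
- Life-threatening = intracranial OR (haemodynamic compromise AND that compromise requires intervention).
- Non-life threatening = major AND NOT life-threatening.

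**Every kind of fatal bleed under these rules**

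| Fatal bleed | Major? | Class under the stated rule |
|---|---|---|
| Intracranial | yes | life-threatening |
| Extracranial, haemodynamic compromise requiring intervention | yes | life-threatening |
| Extracranial, haemodynamic compromise not requiring intervention | yes | non-life threatening |
| Extracranial, no haemodynamic compromise | yes | non-life threatening |

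The last two rows are deaths in the non-life threatening class. The third row should be close to empty: the text says requiring, not receiving, so a patient who dies of blood loss before treatment still meets the condition. The fourth row is the real gap. A fatal airway bleed that kills by asphyxia rather than by blood loss is an example.

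**Does any other part of the Protocol close the gap?**

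- Synopsis: same split, no definition of life-threatening, so nothing is added.
- Secondary study outcomes: bleeding is a cause-of-death category, but no text links it to the severity class of the bleed.
- Quality Control and Study Organization: the committee's stated remit is the cause of death. It is not given bleed severity and is not told to override the class.
- Analysis of secondary endpoints: major and clinically relevant non-major bleeding are named, and the severity classes are not mentioned.

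The gap therefore stays open.

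**What the gap does not touch**

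- The life-threatening condition does not enter the definition of major, so the total of major bleeds is the same whichever class a fatal bleed falls in.
- Cause of death is recorded and adjudicated independently of the severity class, so the count of deaths due to bleeding is the same too.

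**After the change**

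With life-threatening = fatal OR intracranial OR (haemodynamic compromise AND requires intervention), all four rows become life-threatening, and no fatal bleed can fall in the other class.

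**The case against.** The strongest reply is that the split hardly matters. No objective, model or sample-size argument uses it. The section on secondary endpoints lists only the two bleeding outcomes as safety endpoints, and the presentation of fatal bleeds could be settled in the analysis plan. Bleeding deaths are visible through the adjudicated cause of death, and death itself is the co-primary outcome. Most fatal extracranial bleeds will also involve haemodynamic compromise requiring intervention and so be classed correctly.

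Most of this stands, and it limits the point to a minor one. It does not remove it. The Protocol does not leave the definition open; it states one, and an analysis plan that follows it would carry the wrong label forward. The Statistical methodology section also commits to using all collected variables and all derived parameters, which takes in this sub-class even though no table is named for it.

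Three stronger readings are tempting, and the document does not support them.

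- A reader might infer that the primary safety outcome is understated or that bleeding deaths are hidden. They are not: every fatal bleed counts as major, and cause of death is recorded separately. Nor is the lower class a mild one. It is still major bleeding; milder events form the separate non-major outcome.
- A reader might infer that a fatal bleed with no haemodynamic data on record is misclassified by this rule. The definition turns on whether compromise requiring intervention was present, not on whether it was documented. Missing records are a data-capture problem.
- A reader might try to put a number on the affected deaths by applying bleeding and fatality rates to the planned 2100 + 2500 + 400 = 5000 patients. The Protocol gives no rate of major bleeding, no fatal share, and no share of fatal bleeds outside both criteria. Any such count would rest wholly on outside assumptions.

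**Conclusion.** The point holds as a minor defect in an outcome definition. As written, a fatal extracranial bleed without haemodynamic compromise requiring intervention is classed as non-life threatening, and nothing in the Protocol reverses that. The conclusion rests on reading the two-part definition as exhaustive, which its wording supports, and on the split having no third category. It needs no numerical assumption.

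Only the descriptive severity classification is affected. The number of events cannot be derived from the Protocol; it is probably small and may be zero.

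**What to change.** In Safety Outcomes, define a life-threatening major bleed as one that is fatal, intracranial, or associated with haemodynamic compromise requiring intervention. Alternatively, keep the present two criteria and make fatal bleeding its own category, so that the split reads fatal, life-threatening but not fatal, and non-life threatening. Either closes the gap; the second also shows fatal bleeds directly. Carry the same wording into the Synopsis, the eCRF completion guidance and the analysis plan.

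The cost is one added word for the first option, or one added category for the second. No visits, sample size or new data are needed, because fatality already has to be known to apply the major bleeding criterion. The change concerns an outcome label and has no bearing on patient care.
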